9.2.4. Treatment Given as a Result of the Event

The event impact in terms of treatment provided will be as either: none, medication administered, non-drug therapy administered, surgery performed, hospitalization, or other (with a specification).

9.2.5. Outcome Assessment

The outcome of the event will be assessed as either: fatal, not recovered/not resolved, recovered/resolved, recovered/resolved with sequelae, recovering/resolving, or unknown. Only one AE per subject is allowed to have an outcome assessment as "death." If there are multiple causes of death for a given subject, only the primary cause of death will have an outcome of death.

9.3. SERIOUS ADVERSE EVENT (SAE) DEFINITION

An SAE is defined as any AE that:

- Results in death
- Is life threatening (the subject is at immediate risk of dying from the adverse experience)
- Requires subject hospitalization or prolongs existing hospitalization
- Results in persistent or significant disability/incapacity
- Is a congenital anomaly/birth defect
- Important medical events that may not result in death, be life-threatening, or require hospitalization may be considered a serious adverse effect when, based upon appropriate medical judgment, they may jeopardize the subject or subject and may require medical or surgical intervention to prevent one of the outcomes listed in this definition.

9.4. **Reporting of Serious Adverse Events**

The Investigator is required to report all SAEs that occur during the time period specified in Section 9.2. Once the Investigator becomes aware of an SAE, he/she must report the SAE to Medical Monitor within 24 hours.

The Medical Monitor may request additional supporting documentation as it becomes available, such as lab reports, electrocardiogram [ECG] reports, discharge summary, hospital notes, etc., if applicable. Additional follow-up information as it becomes available must be reported to the Medical Monitor.

The Investigator is also responsible for reporting all SAEs to the appropriate Institutional Review Board (IRB) in accordance with local laws and regulations. The Investigator is responsible for maintaining documentation in the study file that indicates the IRB has been properly notified.

9.4.1. SAE Follow-Up

All subjects experiencing an SAE, including the discontinued subjects, must be closely followed until sufficient information is obtained to indicate a return to normal status or until the event stabilizes at a level acceptable to the investigator (i.e., recovery, return to baseline status, no further improvement expected, or death).

For each SAE indicated as an unresolved event on the initial report, regardless of whether the subject completed the study or withdrew, the site should submit a follow-up report with updated information.

9.5. EXPECTED/ANTICIPATED EVENTS

Refer to Investigator Brochure for the expected/anticipated events.

9.6. **PREGNANCY REPORTING**

To ensure patient safety, any pregnancy that occurs after the first treatment visit until the end of final study visit should be recorded using a Pregnancy Notification Form and reported immediately to Sponsor within 24 hours of learning of the pregnancy.

If a subject becomes pregnant during the study before the end of treatment phase, they will be a discontinued subject. If a subject becomes pregnant during the study after the end of treatment during the follow up portion, they can complete the remaining scheduled follow up unless there is a medical contraindication.

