- 8. Men and women of childbearing potential and their partner must agree to use two medically accepted methods of contraception (e.g., barrier contraceptives [male condom, female condom, or diaphragm with a spermicidal gel], hormonal contraceptives [implants, injectables, combination oral contraceptives, transdermal patches, or contraceptive rings], or one of the following methods of birth control (intrauterine devices, bilateral tubal occlusion, or vasectomy) or must practice complete sexual abstinence for the duration of the study (excluding women who are not of childbearing potential and men who have been sterilized).
- 9. Females of child-bearing potential must have a negative urine pregnancy test at Screening Visit and prior to receiving the first dose of study drug; and Male participants must agree to use contraception and refrain from donating sperm for at least 90 days after the last dose of study intervention.
- 10. Subject is willing and able to comply with scheduled visits, drug administration plan, laboratory tests, other study procedures and study restrictions.

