4. STUDY SCHEDULE

The study Schedule of Assessments is presented in Table 4-1 and Table 4-2.

The study will have three phases: Screening Phase, Treatment Phase, and Follow-Up Phase.

Note: During visits conducted at the study clinic, subjects and site personnel will use appropriate protective gear (e.g., masks, gloves) to prevent the spread of the infection.

Screening Phase (up to 1 week):

All subjects will provide written informed consent and have a Screening visit (V1) within 7 days prior to first treatment visit (V2) to determine eligibility for subject participation.

All subjects who fail to meet eligibility criteria are considered screen failures and are exited from the study without further evaluation.

Treatment Phase (12 weeks):

Ampligen[®] and placebo will be administered via twice weekly infusions (Example: Monday/Thursday or Tuesday/Friday schedule) for 12 weeks.

Follow-Up Phase (2 weeks):

Two safety follow-up visits will be performed 3 to 4 days and 2 weeks after the End of Treatment (EOT) visit (V25).

Procedure/Assessments	Screening Visit						Treatn	ient Vi	sits					
Visit	V1	V2	V3	V4	V5	V6	V 7	V8	V9	V10	V11	V12	V13	V14
Week	Week 0	1(Day 0)	1	2	2	3	3	4	4	5	5	6	6	7
Window Period		Within 7 days of SV												
	Х													
	Х	Х												
	Х													
	Х	Х												
	Х	Х	Х	X	Х	Х	Х	Х	Х	Х	Х	Х	X	X
	Х	Х	Х	X	X	Х	X	Х	Х	Х	Х	Х	X	Х
	Х	Х										Х		
	Х	Х										Х		
	Х	Х		X		Х		Х		Х		Х		X
		х		Х		Х		х		Х		х		х
		х		Х		х		х		х		х		x
		Х	х	Х	Х	Х	Х	х	Х	Х	Х	х	Х	х
		Х	х		Х		х		х		Х		Х	
	Х	Х		Х		Х		Х		Х		Х		Х
		Х						Х						
	Х					Х						Х		
	Х	Х	Х	Х	Х	Х	Х	Х	Х	Х	Х	Х	Х	Х
		Х	Х	Х	Х	Х	Х	Х	Х	Х	Х	Х	Х	Х
		Х	Х	Х	Х	Х	Х	Х	Х	Х	Х	Х	Х	Х
	х													
	X	Х										Х		
Bio	Х	Х										Х		
	Х	Х						Х	Х					
	Х	X										Х		

Table 4-1:Schedule of Assessments V1 to V14

CONFIDENTIAL

xx x
Image: Constraint of the state of the st

Screening Visit

V1

Week 0

V2

1(Day 0)

V3

1

V4

2

V5

2

V6

3

Procedure/Assessments

Visit

Week

6

V14

7

V11 V12 V13

6

Treatment Visits

V8

4

V9

4

V10

5

5

V7

3

 Table 4-2:
 Schedule of Assessments V15 to V27

Procedure/Assessments		Treatment Visits											Follow-up 2
Visit	V15	V16	V1 7	V18	V19	V20	V21	V22	V23	V24	V25	Visit 26	Visit 27
Week	7	8	8	9	9	10	10	11	11	12	12	Week 13 (3 to 4 days after EOT)	Week 14
Window Period													± 3 days
	Х	Х	Х	Х	Х	Х	Х	Х	Х	Х	Х	Х	Х
	Х	Х	Х	Х	Х	Х	Х	Х	Х	Х	Х	Х	Х
										Х			Х
										Х			X

V25	Visit 26	Visit 27
	Follow-up 1	Follow-up
	Date: 2	3-Aug-2023

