4.2.2. Subsequent Treatment Visits (V3-V25)

The following assessments will be performed:

- **4.3.** FOLLOW-UP PHASE
- **4.3.1.** Follow-Up visit 1 (V26)

Follow-Up visit (V26) will be performed 3 or 4 days after the End of Treatment (EOT) visit (visit 25). The following assessments will be performed at V26:

Follow-Up visit 2 will be performed at 2 weeks after the End of Treatment (EOT) visit (visit 25). The following assessments will be performed at V27:

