9.6.2. Informed Consent

The ICF will include information regarding reporting of pregnancy to the Sponsor and collection of information through the end of pregnancy that occurs in either a female subject or in a female partner of a male subject. If a female partner becomes pregnant, the Investigator will request consent from the partner to collect this information.

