9.6.3. Pregnancy Follow-Up

The pregnancy will be followed-up to determine the outcome (spontaneous miscarriage, elective termination, ectopic pregnancy, normal birth, or congenital abnormality) and should include an assessment of the possible relationship to the study treatment of any pregnancy outcome. This information should also be documented on the Pregnancy Outcome Form and reported to the Sponsor.

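### Section 9.6 dates pregnancy reporting only to the final study visit, so for men dosed through V25 a partner pregnancy conceived in the last 73 to 79 days of the 90-day male precaution period has no express reporting duty in the visible protocol

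*Protocol*

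**What the plan says.** Four parts of the protocol bear on this.

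- **Reporting duty.** Section 9.6 (Pregnancy Reporting) states that "any pregnancy that occurs after the first treatment visit until the end of final study visit should be recorded using a Pregnancy Notification Form", with notice to the sponsor within 24 hours of learning of it. This is the only place where a date range is attached to reportable pregnancies.
- **Precaution period.** Inclusion criterion 9 (section 3.3.1) reads "Male participants must agree to use contraception and refrain from donating sperm for at least 90 days after the last dose of study intervention".
- **Final visit.** Section 4 states "Two safety follow-up visits will be performed 3 to 4 days and 2 weeks after the End of Treatment (EOT) visit (V25", and section 4.3 repeats that "Follow-Up visit 2 will be performed at 2 weeks after the End of Treatment (EOT) visit (visit 25". Table 4-2 gives V27 a window of ±3 days.
- **Partners.** Section 9.6.2 says the consent form will cover reporting and information collection for a pregnancy "in either a female subject or in a female partner of a male subject", and adds "If a female partner becomes pregnant, the Investigator will request consent from the partner to collect this information". Section 9.6.3 says "The pregnancy will be followed-up to determine the outcome", with the result to go to the sponsor. Neither section says when a pregnancy must begin in order to count.

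**The concern.** The protocol sets its own period of precaution for men, at least 90 days after the last dose, and it treats partner pregnancies as information worth collecting. A conception in that period is what the precaution is meant to prevent, and so one the sponsor would want to hear about. Yet the only dated duty stops at V27, about two weeks into the period. A site that follows section 9.6 as written would have no stated obligation to notify the sponsor of a partner pregnancy conceived after V27, or to follow it to its outcome. What is at stake is completeness of safety information on paternal exposure. No endpoint, sample size or efficacy analysis depends on it.

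**Working it through.** This is calendar arithmetic followed by a check of the neighbouring text.

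**Inputs**
- Screening 1 week, treatment 12 weeks, follow-up 2 weeks (synopsis, Study Duration).
- Two infusions a week for 12 weeks (section 6.2); treatment visits V2 to V25 (section 4.2).
- V27 at 14 days after V25 (sections 4 and 4.3), window ±3 days (Table 4-2).
- Male precaution period of at least 90 days after the last dose (inclusion 9).

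**Reproducing the plan's timeline**
- Total duration: 1 + 12 + 2 = 15 weeks, which agrees with the synopsis figure of up to 15 weeks.
- Dosing visits: 25 − 2 + 1 = 24 = 12 × 2, so V25 carries the last planned dose. Days after V25 are then days after the last dose.

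**Length of the gap** = 90 − (day of V27 after V25)

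| V27 on day | Days left of the 90 | Share of the 90 |
|---|---|---|
| 11 | 90 − 11 = 79 | 79/90 = 88% |
| 14 | 90 − 14 = 76 | 76/90 = 84% |
| 17 | 90 − 17 = 73 | 73/90 = 81% |

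Because inclusion 9 sets 90 days as a floor, these are minimum figures for a man who takes the V25 dose.

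**Does other text close the gap?**
- Section 9.2 runs AE and SAE reporting from the first treatment visit to the final study visit, and section 9.4 ties required SAE reports to that same period. Section 9.6.1 classes congenital abnormalities and miscarriages as SAEs but sets no later date. These sections do not expressly reach an adverse outcome of a partner pregnancy conceived after V27.
- Section 9.6.2 describes what the consent form will contain and how partner consent is sought. Its reference to the end of pregnancy says how long a pregnancy is followed, not which pregnancies qualify.
- Section 9.6.3 governs follow-up to outcome and adds no onset window.

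**Two readings of section 9.6**
1. Its dated sentence covers partners, because it speaks of any pregnancy and 9.6.2 puts partners in scope. The window then closes at V27, leaving 73 to 79 days.
2. Its dated sentence covers subjects only. The protocol then states no onset window for partners at all.

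Under neither reading does a visible sentence make a partner pregnancy conceived between V27 and day 90 expressly reportable. Under the second, the defect is an undefined window rather than one that closes early.

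**The case against.** The best counter-argument is that section 9.6 never mentions partners. It gives patient safety as its purpose, and its next paragraph deals only with a subject who becomes pregnant. Partners are handled in 9.6.2 and 9.6.3, which carry no end date, so partner collection could be read as open-ended. That stands in part: the text is ambiguous, and an undated provision does not exclude the later period. It does not supply an express duty either, since those sections concern consent content and outcome follow-up.

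Second, section 9.6.2 sends the reporting information to the consent form, which is where a man would learn whether and for how long to report. The consent form and the Pregnancy Notification Form are not available here, and the V26 and V27 procedure lists are blank in the public text. This stands: the point can be made only about the visible protocol, and the practical gap may be smaller.

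Third, nothing in the documents requires the reporting window to equal the precaution window. That is true, and it is why this is a design improvement rather than a contradiction. The recommendation rests on the protocol's own choice of 90 days.

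Fourth, the 73 to 79 days apply only to men dosed through V25. For those who stop early, the interval from last dose to final visit is not fixed by the visible text, although section 5.4 asks for follow-up attempts. No figure is offered for them.

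**Conclusion.** The point holds, as a minor one. For men dosed through V25, the reporting duty dated in section 9.6 ends 11 to 17 days after the last dose, and the remaining 73 to 79 days of the 90-day precaution period carry no express duty to report a partner pregnancy. This assumes that the last dose is at V25, that V27 falls within its window, and that text not available for review does not add the duty.

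A reader might infer more, and the documents do not support it:
- *That later partner pregnancies are barred from being reported.* Nothing forbids such a report.
- *That pregnancies beginning by V27 are lost.* Section 9.6 dates a pregnancy by when it occurs, and 9.6.3 follows it to outcome, so one discovered after V27 can still be covered.
- *That female subjects have the same gap.* The 90-day term in inclusion 9 is addressed to men.
- *That a given number of events will be missed.* The documents give neither the number of men nor a pregnancy rate, so any such figure would be assumption. A late report would probably be rare.

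**What to change.** Amend section 9.6 to say that a pregnancy in the female partner of a male subject is reportable if it occurs after the first treatment visit and up to at least 90 days after his last dose, and that sections 9.6.1 and 9.6.3 apply to it even when this falls after the final study visit. Dating the window from the last dose also settles the case of men who stop early.

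Have male subjects told to notify the site if a partner becomes pregnant in that period. Consent wording needs changing only if the form does not already say this.

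The cost is a small wording amendment with its ethics review, and possibly a rare late report to process. No extra visit or scheduled contact is needed, and design, sample size and analysis stay as they are.

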9.6.1. AE and SAE Reporting

Pregnancy itself is not regarded as an AE unless there is a suspicion that the IP may have interfered with the effectiveness of a contraceptive medication. Congenital abnormalities/birth defects and spontaneous miscarriages should be reported and handled as SAEs.

9.6.1.1. Abortions

An induced elective abortion to terminate a pregnancy without medical reason is not regarded as an AE. However, an induced therapeutic abortion to terminate a pregnancy because of complications or medical reasons must be reported as an SAE. The underlying medical diagnosis for this procedure should be reported as the SAE term. A spontaneous abortion in a study subject is always considered an SAE.

9.6.2. Informed Consent

The ICF will include information regarding reporting of pregnancy to the Sponsor and collection of information through the end of pregnancy that occurs in either a female subject or in a female partner of a male subject. If a female partner becomes pregnant, the Investigator will request consent from the partner to collect this information.

9.6.3. Pregnancy Follow-Up

The pregnancy will be followed-up to determine the outcome (spontaneous miscarriage, elective termination, ectopic pregnancy, normal birth, or congenital abnormality) and should include an assessment of the possible relationship to the study treatment of any pregnancy outcome. This information should also be documented on the Pregnancy Outcome Form and reported to the Sponsor.

10. DIRECT ACCESS TO SOURCE DATA/DOCUMENTATION

Subjects will be identified on eCRFs by a unique subject identification number and on source documents by name and date of birth. No personal identifier will be used in any publication or communication used to support this research study. The subject identification number will be used if it becomes necessary to identify data specific to a single subject.

The local IRB, FDA, the monitors, auditors, and personnel authorized by the Sponsor are eligible to review the medical and research records related to this study as part of their responsibility to protect human subjects in clinical research. They will be given direct access to source data and documentation (e.g., medical charts/records, printouts etc.) for source data verification, provided that subject confidentiality is maintained in accordance with local requirements. Access to electronic medical records may be governed by institution policy. The study site will be required to ensure access while remaining compliant with institutional requirements.

11. QUALITY CONTROL AND QUALITY ASSURANCE

11.1. MONITORING REQUIREMENTS

The specific obligations outlined in 21 Code of Federal Regulations (CFR) and ICH guidelines require the Sponsor to maintain current personal knowledge of the progress of a study. Therefore, the Sponsor's designated monitor will visit the site during the study as well as maintain frequent telephone and written communication. The Investigator will permit the Sponsor to monitor the study as frequently as is deemed necessary and provide access to medical records to ensure that data are being recorded adequately, that data are verifiable, and that protocol adherence is satisfactory.

As delineated above, the Investigator will permit representatives of the Sponsor and/or designated CRO to inspect all CRFs and corresponding study subject original medical records (source documents) at regular intervals throughout the study. Subject original medical records and other relevant data must be available to support all data recorded in the eCRF. In addition to the original medical records, these data may include but are not limited to study, laboratory reports, etc.

In accordance with federal regulations, site inspections will serve to verify strict adherence to the protocol and the accuracy of the data that is being entered on the case report forms. A Monitoring Log will be maintained at each study site. The Monitoring Log will be signed by the monitor, dated, and stated the type of visit. The Investigator should be aware that the study site and subject records may be inspected by the Sponsor and or representatives of the designated CRO, FDA or other regional regulatory authority.

11.2. ACCEPTABILITY OF CASE REPORT FORMS (CRFs)

For each subject who has signed an informed consent form, a CRF must be completed. For subjects who are screen failures, this would be limited to the screen failure CRF page. All source documents and CRFs will be completed as soon as possible after the subject's visit and corrections to data on the CRFs will be documented, if applicable. The Investigator will review the CRFs to indicate that, to his/her knowledge, they are complete and accurate. CRFs will be reviewed by the Sponsor's or designated CRO's monitor, who will make a decision as to their acceptability.

11.3. MODIFICATION OF PROTOCOL

The Investigator will not modify or alter this protocol without first obtaining the concurrence of the Sponsor. Approval by the Investigator's IRB must also be obtained prior to implementation of the change, with two exceptions:

- 1. When necessary to eliminate apparent immediate hazard to the subject; or
- 2. When the modification does not involve the subject's participation in the trial.

An amendment may also require modification of the informed consent form. The Investigator will provide an approval letter for the amendment and revised informed consent form, if applicable, to the Sponsor. An amendment must be provided in writing, and it must be dated by both the Sponsor and the Investigator. If necessary, the Sponsor will submit protocol amendments to FDA and other appropriate regulatory authorities and notify other Investigators using this protocol.

11.4. Reporting Protocol Deviations

The Investigator is obligated to follow the protocol without departure from the requirements written in the protocol. If the Investigator deviates from the protocol requirements, the Sponsor will make the determination as to whether the subject will continue in the study. The Sponsor also has the right to discontinue the subject for protocol violations. The IRB may also have to be contacted if safety to the subject or if the scientific soundness of the study is involved. All protocol deviations must be documented in the CRFs.

11.4.1. Major Protocol Deviation or Violation

A major protocol deviation or violation is a deviation from the IRB approved protocol that may affect the subject's rights, safety, or well-being and/or the completeness, accuracy, and reliability of the study data. Examples of this include:

- Failure to obtain informed consent prior to initiation of study-related procedures
- A research subject does not meet the protocol's eligibility criteria but was enrolled without prior approval from the sponsor.
- A research subject received the wrong treatment or incorrect dose.
- A research subject met withdrawal criteria during the study but was not withdrawn.
- A research subject received a prohibited concomitant medication.
- Failure to treat research subjects per protocol procedures that specifically relate to primary efficacy outcomes.
- Changing the protocol without prior sponsor and IRB approval.
- Multiple minor violations of the same nature after multiple warnings.

11.4.2. Minor Protocol Deviation or Violation

A minor protocol deviation is any change, divergence, or departure from the study design or procedures of a research protocol that has not been approved by the IRB and which DOES NOT have a major impact on the subject's rights, safety or well-being, or the completeness, accuracy, and reliability of the study data. Examples of this include:

• Follow-up visits that occurred outside the protocol required time frame because of the participant's schedule.

• Blood samples obtained at times close to but not precisely at the time points specified in the protocol.

